1.2.8.2 NCI trials of LMB-100

1.2.8.2.1 Mesothelioma, short infusion

Single agent LMB-100 has been tested in two additional ongoing Phase I studies. A 30-minute infusion given on days 1, 3 and 5 of a 21-day cycle was given to 10 mesothelioma patients (NCT02798536). At 170 mcg/kg, multiple patients experienced reversible acute kidney dysfunction which prolonged hospitalization. For this reason, **single agent MTD of 140 mcg/kg was established**. Toxicities and peak drug levels were similar to the Roche study (manuscript in preparation).

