1.2.8.2.3 Pancreatic cancer and other MSLN-expressing malignancies, long infusion

Since some pre-clinical studies suggested that duration of exposure to LMB-100 may be more important to anti-tumor activity than peak drug levels (data not shown), a new study was initiated to investigate the safety and efficacy of LMB-100 given in a long infusion format to patients with pancreatic cancer and other mesothelin-positive solid tumor malignancies (NCT02810418). As of

[figure not shown]
August 2018, 15 participants were enrolled on this study (12 with pancreatic adenocarcinoma, 1 with ampullary cancer, 1 with pleural mesothelioma, 1 with rectal cancer). For this study, patients received only two cycles of study drug by design. Neither toxicity nor efficacy were observed in the 3 patients treated at the initial dose level of 65 mcg/kg/day given over 48 hrs starting on Day 1 of each 21-day cycle. Pharmacokinetic measurements were erratic, likely secondary to inability of the syringe pumps to deliver such small volumes of drug, or due to presence of pre-existing anti-PE antibodies that acted as a drug sink in some patients. In subsequent dose levels, participants were treated with an initial 40 mcg/kg loading dose over 30 minutes prior to the start of the long infusion. Single agent MTD of 100 mcg/kg/day x48hrs preceded by 40 mcg/kg loading dose was established. DLT of grade 3 proteinuria was noted in 1/6 patients treated at this dose level. 3/6 patients at this dose level developed non-dose-limiting VLS that included weight gain >5kg, as well as hypotension (grade 2). The dose escalation was halted at this point to consider a more tolerable alternative schedule. Subsequently, a dose of 100 mcg/kg/day x24hrs preceded by 40 mcg/kg loading dose given on days 1 and 4 was tested. Two patients receiving this dose experienced no drug-related toxicity. One additional patient required hold of the D4 dose due to transient grade 2 rise in creatinine, which was considered an investigator-specified DLT. Three additional patients were unable to receive the D4 dose due to medical complications related to their cancer. These 3 patients receiving only the D1 dose also experienced no drug-related DLT or VLS.

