3.1.1 Dose Limiting Toxicity

For the study, a DLT will be defined as any of the following events occurring during the first cycle of treatment (21 days), the DLT evaluation period. Toxicities determined to be unequivocally related to disease progression or intercurrent illness will not be regarded as DLTs. The following will be considered DLTs:

- Any death not clearly due to the underlying disease or extraneous causes
- Transaminitis that meets criteria for Hy's Law: grade ≥2 elevation of AST or ALT with simultaneous elevation of total bilirubin to ≥ 2x ULN while alkaline phosphatase remains < 2x ULN.

Hematological toxicities:

- Grade 4 neutropenia (i.e. absolute neutrophil count (ANC) <0.5 x 10^3 cells/µL for a minimum duration of 7 days)
- Grade 3 and 4 febrile neutropenia (i.e. ANC < 1.0×10^3 cells/µL with a single temperature of >38.3°C or a sustained temperature of ≥38°C for more than one hour; or life-threatening consequences with urgent intervention indicated)
- Grade 4 thrombocytopenia ($\leq 25.0 \times 10^3 \text{ cells/}\mu\text{L}$)
- Grade 3 thrombocytopenia associated with bleeding episodes
- Grade 4 anemia

$\underline{\text{Grade} \geq 3 \text{ non-hematological toxicity with the exception of:}}$

- Grade 3 nausea and vomiting lasting <48 hours occurring in the absence of appropriate anti-emetic treatment
- Grade 3 diarrhea lasting for ≤ 2 days with no fever or dehydration
- Infusion-related reactions up to and including Grade 3. IRRs are not considered to be DLTs since, based on experience with monoclonal antibodies, they are idiosyncratic and not dose-related events. Precautions will be taken if IRRs Grade ≥2 occur (see Section 3.3).
- Asymptomatic grade 3 elevation of ALT, AST, GGT, bilirubin or alkaline phosphatase attributable to study drug that persists for less than 7 days if not violating Hy's Law. (Please note that all grade 4 elevations in these parameters should be considered a DLT)
- Asymptomatic laboratory values (other than ALT, AST, GGT, bilirubin, alkaline phosphatase or creatinine) of Grade 3 that are judged not clinically significant by the investigator.
- Isolated Grade 3 fever (without signs and/or symptoms of an infection) occurring within 48 hours after LMB-100 infusion and resolving within 48 hours to \leq Grade 2 and fully resolved within 1 week.

Other toxicities:

- Any other drug related toxicity considered significant enough to be qualified as a DLT in the opinion of the principal investigator.

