Renal toxicity	In the event of Grade 1 or greater renal toxicity consider increasing oral or intravenous hydration, and consider delaying LMB-100 administration by up to 48hrs.			
	In the event of Grade 2 or greater renal toxicity hold LMB-100 administration until recovery to Grade 1 or better. If this does not occur within 48hrs, no further LMB-100 should be given during the cycle.			
IRR = infusion related reaction; IV =	= intravenous; CTCAE = Common Terminology Criteria for Adverse			

Events

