10.3 POPULATIONS FOR ANALYSES

10.3.1 Evaluable for toxicity

All patients who receive treatment during dose escalation will be reported. Any patient who receives any study drug treatment and experiences a DLT related to study drug within 21 days of initial treatment is evaluable. Otherwise, patients evaluable for DLT must: 1) receive all doses of study drugs, 2) be followed for study drug toxicity for at least 21 days after the administration of the first dose of LMB-100.

In the expansion phase, up to 15 evaluable patients who can have their drug levels assessed in cycle 2 will be included in analyses. Up to 5 patients will be replaced if they have PD before C2, but if more than 5 patients progress before C2, then no further patients will be accrued as soon as this can be determined.

10.3.2 Evaluable for objective response:

Only those patients who have measurable disease present at baseline, have received at least one cycle of therapy, and have had their disease re-evaluated will be considered evaluable for response. These patients will have their response classified according to the definitions stated below. (Note: Patients who exhibit objective disease progression prior to the end of cycle 1 will also be considered evaluable.) Responses or progressions noted in patients receiving treatment extension will be recorded in the study database but will not be reported in the aggregate objective response rate, which only corresponds to assessments taken prior to the start of a 4th cycle.

10.3.3 Evaluable Non-Target Disease Response:

Patients who have lesions or tumor marker present at baseline that are evaluable but do not meet the definitions of measurable disease, have received at least one cycle of therapy, and have had their disease re-evaluated will be considered evaluable for non-target disease. The response assessment is based on the presence, absence, or unequivocal progression of the lesions or increase in tumor marker.

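### The DLT evaluability rule has no exception for doses lost to drug toxicity, so a patient with a toxicity-curtailed cycle 1 and no declared DLT leaves the 3+3 count; this can bias the MTD upward

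*Combined protocol and SAP*

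**What the plan says.** Section 10.3.1 gives two routes to DLT evaluability. The first is to have a DLT: "Any patient who receives any study drug treatment and experiences a DLT related to study drug within 21 days of initial treatment is evaluable". The second is for everyone else: "Otherwise, patients evaluable for DLT must: 1) receive all doses of study drugs", together with 21 days of follow-up from the first LMB-100 dose. The second route does not ask why a dose was missed, and does not say that the doses meant are those of cycle 1. The same section also says: "All patients who receive treatment during dose escalation will be reported".

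Table 12 in 3.3.1 contains a rule that curtails the cycle: "In the event of Grade 2 or greater renal toxicity hold LMB-100 administration until recovery to Grade 1 or better". It continues: "If this does not occur within 48hrs, no further LMB-100 should be given during the cycle".

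Section 3.1.1 makes grade 3 or higher "non-hematological toxicity with the exception of" a list of exemptions an automatic DLT. Grade 2 renal toxicity is below that line. Two further clauses in 3.1.1 have no grade floor. The principal investigator may call any significant drug-related toxicity a DLT, and a drug-related failure to start cycle 2 within two weeks of completing cycle 1 is a DLT.

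Section 10.2 sets an accrual ceiling of 45 against 27 evaluable patients. The ceiling is there partly for treated patients who do not complete the DLT period.

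**The concern.** Taken together, these rules create a patient with drug toxicity, curtailed cycle 1 dosing, no automatic DLT and no place in the 3+3 count. Whether that patient is counted depends on a case-by-case judgement made after the event. Exclusion for a reason related to tolerability is informative, and it bears on the escalation phase's primary endpoint, the MTD. With three patients per cohort, one such classification can turn 1 of 3 into 0 of 3.

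The toxicity concerned is the one most relevant to this drug. In the earlier mesothelioma study at 170 mcg/kg, "multiple patients experienced reversible acute kidney dysfunction which prolonged hospitalization", and this set the single-agent MTD at 140 mcg/kg, which is dose level 2 here (Table 8). In another LMB-100 study the protocol records: "One additional patient required hold of the D4 dose due to transient grade 2 rise in creatinine, which was considered an investigator-specified DLT". That decision has not been carried into the DLT list.

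Renal toxicity is not the only route. Infusion reactions up to grade 3 are exempt from DLT in 3.1.1, yet Table 12 has one line that resumes a grade 3 infusion and another that does not restart it. Section 12.1.2 names treatment-limiting toxicity beside DLT, but nothing says how it enters the count. The expansion safety rule in 10.4.4 counts only DLTs, so undeclared dose loss is not caught there either.

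A smaller matter is that cycle 1 contains 10 × 2 = 20 tofacitinib doses. Read literally, one dose not received makes a patient without a DLT non-evaluable.

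**Working it through.** The plan states no figure on this point, so there is none to reproduce. The check is how the count responds to each way of handling these patients.

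**Inputs from the documents.** Escalation proceeds on 0 of 3 or at most 1 of 6 DLTs (3.1.2, 10.2). At least six patients are needed at the recommended dose, with at most one DLT (Table 9). The MTD is the highest dose with a DLT rate below 33% (10.2).

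**Assumed inputs.** Let p be the probability of a DLT, and q the probability of losing cycle 1 doses to drug toxicity without a declared DLT; the two are mutually exclusive. The documents give neither. The kidney events in 1.2.8.2.1 carry no grade or count, and they occurred above the highest planned dose.

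**DLT probability x that enters the count**
- Excluded and replaced: x = p/(1 − q)
- Kept and counted as DLT: x = p + q
- Kept and counted as non-DLT: x = p

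**Probability of passing a level.** P(x) = (1 − x)³ + 3x(1 − x)⁵. This takes it that 1 of 3 always leads to three more patients, although Table 9 also lets the investigator stop there.

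For p = 10% and q = 20%:
- Excluded: x = 0.10/0.80 = 0.125; P = 0.670 + 0.192 = 0.862
- Counted as DLT: x = 0.30; P = 0.343 + 0.151 = 0.494
- Counted as non-DLT: x = 0.10; P = 0.729 + 0.177 = 0.906

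Over a range of assumptions:

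| p | q | Excluded | Counted as DLT | Counted as non-DLT |
|---|---|---|---|---|
| 10% | 5% | 89.7% | 81.4% | 90.6% |
| 10% | 10% | 88.7% | 70.9% | 90.6% |
| 10% | 20% | 86.2% | 49.4% | 90.6% |
| 10% | 33.3% | 81.4% | 25.8% | 90.6% |
| 20% | 5% | 68.6% | 60.0% | 70.9% |
| 20% | 10% | 66.0% | 49.4% | 70.9% |
| 20% | 16.7% | 62.2% | 36.6% | 70.9% |
| 20% | 33.3% | 49.4% | 13.7% | 70.9% |

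In this table, exclusion rather than counting as DLT raises the pass probability by about 8 points (89.7 − 81.4) to 56 points (81.4 − 25.8). Exclusion rather than counting as non-DLT lowers it by about 1 to 22 points (70.9 − 49.4).

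**Highest level.** The six-patient requirement gives (1 − x)⁶ + 6x(1 − x)⁵. At p = 10% and q = 20% this is 83.3% excluded, 42.0% counted as DLT and 88.6% counted as non-DLT. The pattern is the same.

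**Direction of bias.** Let r be the DLT probability that the excluded patients would have had under full dosing. The full-dosing DLT rate is then p + qr. Exclusion understates it when p/(1 − q) < p + qr, that is, when r > p/(1 − q). At p = 10% and q = 20% the break-even is 12.5%; at p = 20% and q = 16.7% it is 24%.

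**Replacements.** To reach three evaluable patients takes 3/(1 − q) − 3 extra, which is 0.75 at q = 20%.

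**The case against.** The strongest reply is that exclusion is not automatic. The discretionary clause in 3.1.1 has no grade floor, and a patient declared to have a DLT is evaluable under 10.3.1 after any study drug. The grade 2 creatinine case in 1.2.8.2.3 shows an investigator doing exactly this. That stands, and a reader who infers that every such patient is replaced goes beyond the text. It does not close the gap, because the classification behind a primary endpoint is left to judgement after the event. The delay clause helps less: it misses a patient who loses doses, recovers and starts cycle 2 on time. It may also be met only up to day 21 + 14 = 35, whereas 10.3.1 refers to DLTs within 21 days of initial treatment.

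Replacement during escalation is inferred from the accrual ceiling. The only explicit replacement sentence in 10.3.1 concerns progression before cycle 2 in the expansion. This is conceded.

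A reader might also infer that the rule as such biases the MTD upward, and that 86% against 49% measures its effect. The documents support neither. The 49% requires every such patient to be classified as a DLT, so the contrast combines evaluability with a changed DLT definition. Against counting them as non-DLTs, exclusion makes passing less likely.

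Nor are these patients lost to safety review. All treated escalation patients are reported, toxicities are tabulated by grade and type at each level (10.4.4), and the monitoring committee reviews adverse events after the first five subjects (7.4.3). A dose below the MTD may be taken into expansion if chronic toxicity is judged intolerable (10.2). What is lost is their place in the count that drives escalation.

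On tablets, 3.2.1 tells patients to take a skipped dose as soon as possible, and nursing gives tofacitinib to inpatients, so a skipped dose is not always a dose not received.

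**Conclusion.** The concern holds in conditional form. Section 10.3.1 removes from the 3+3 count a patient who loses cycle 1 doses to drug toxicity and has no declared DLT, and Table 12 makes that patient reachable at a grade below the automatic DLT line. This can bias the MTD upward if such patients are dose limiting, or if their DLT probability under full dosing exceeds p/(1 − q). The second is plausible for patients already showing toxicity, but the documents give no figure for it. With assumed rates of 10% and 20%, the handling alone moves the pass probability between 49% and 91%, and exclusion gives 86%. These figures show how much depends on an unspecified choice; they do not estimate the bias in this trial.

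**What to change.** Reconcile 3.1.1, Table 12 in 3.3.1, 10.3.1 and 12.1.2, and amend 10.3.1 as follows:

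- (a) Only patients who miss cycle 1 doses for reasons unrelated to study drug may be replaced, and this is stated explicitly for the escalation phase.
- (b) A patient who loses cycle 1 doses to study drug toxicity stays in the 3+3 count, classified by a rule fixed in advance. Which toxicities are dose limiting is the sponsor's clinical decision; the statistical requirement is that it be made before the data are seen.
- (c) The dosing requirement is limited to cycle 1, and for tofacitinib it becomes a minimum exposure stated by the sponsor, so that one missed tablet does not remove a patient.

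The cost is a few sentences of text, with no added visits or sample size. The downside is that escalation may stop at a lower level somewhat more often, depending on the classification chosen under (b).

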1.1.2 Secondary Objectives

- For the dose escalation cohort: To determine whether co-administration of tofacitinib delays formation of neutralizing anti-LMB-100 ADAs through cycle 2 of treatment (as measured by LMB-100 serum drug levels)
- For the expansion cohort: To assess the safety and tolerability of the combination in patients with pancreatobiliary cancer
- For both cohorts: To define the effect of tofacitinib on the pharmacokinetic characteristics of LMB-100
- For both cohorts: To determine the percentage of patients who have delayed formation of neutralizing anti-LMB-100 ADAs through cycle 3 of treatment (as measured by LMB-100 serum drug levels) when co-administered tofacitinib

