10.1.2 Secondary Endpoints

The secondary endpoints for both the dose expansion and dose escalation cohorts are the LMB-100 peak serum level, half-life and AUC during cycle 1, and the percentage of participants with EOI LMB-100 serum drug concentration that meets threshold during cycle 3. For the dose escalation cohort, the percentage of participants with EOI LMB-100 serum drug concentration that meets threshold during cycle 2 of treatment will also be measured. For the dose expansion cohort, the number and description of adverse events by grade will also be reported.

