10.4.9 Exploratory Analyses

The following are the intended exploratory analyses focusing on the patients in the expansion cohort:

Disease control rate (DCR) at 9 weeks will be estimated along with a 95% confidence interval. PFS and OS will be estimated by the Kaplan-Meier method, along with 95% confidence intervals. Changes in appropriate tumor markers with treatment (if applicable to patient's tumor type) will be determined and tested for change from baseline using a Wilcoxon signed rank test. Titer of free anti-LMB-100 antibodies at the start of each cycle and following completion of treatment will be obtained and results reported descriptively; the relationship of these values with peak serum drug levels of LMB-100 will be explored. Association of response with tumor MSLN expression will be done by comparing levels between responders and non-responders using an appropriate nonparametric test such as a Cochran-Armitage test or Fisher's exact test. Changes in circulating endothelial cells following immunotoxin treatment, changes in serum cytokines following immunotoxin treatment, and changes in tumor microenvironment following immunotoxin treatment will be reported descriptively, with statistical testing of changes as appropriate. Any statistical tests performed on the exploratory endpoints will have results presented without formal adjustment but interpreted in the context of the number of tests performed. In patients receiving treatment extension, the anti-drug antibodies and peak plasma LMB-100 drug levels will be obtained at each cycle after cycle 3 and reported with descriptive statistics. The levels of these

measures after cycle 3 may be compared descriptively to those in earlier cycles for purposes of evaluating the effect of the agent in this small subset of patients.

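### Section 10.3.1 names no all-treated safety set for the expansion: read literally, its adverse event tables cover only patients with a cycle 2 drug level

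*Combined protocol and SAP*

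**What the plan says.** Section 10.3.1 treats the two phases differently. For escalation: "All patients who receive treatment during dose escalation will be reported". For the expansion: "In the expansion phase, up to 15 evaluable patients who can have their drug levels assessed in cycle 2 will be included in analyses". It then adds: "Up to 5 patients will be replaced if they have PD before C2". If more than 5 progress before cycle 2, accrual stops.

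Safety is a declared aim of the expansion. Section 1.1.2 lists: "For the expansion cohort: To assess the safety and tolerability of the combination in patients with pancreatobiliary cancer". Section 10.2 gives safety of the optimal dose as the first purpose of the additional patients. The matching endpoint in 10.1.2 reads: "For the dose expansion cohort, the number and description of adverse events by grade will also be reported". Section 10.4.3 plans percentages and counts for the secondary endpoints but names no denominator for adverse events. For efficacy, 10.4.9 says "PFS and OS will be estimated by the Kaplan-Meier method" and refers to patients in the expansion cohort without naming an analysis set.

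**The concern.** The cycle 2 drug-level set suits the primary endpoint, because a patient who never reaches cycle 2 has no level to classify. It does not suit a safety endpoint. Leaving in cycle 1 is itself a tolerability outcome, so a set that requires a cycle 2 level selects on the thing being measured. The sentence stands under a toxicity heading, refers to analyses in general, and has no all-treated counterpart of the kind given for escalation. An analyst who follows 10.3.1 as written would drop treated patients from the expansion adverse event tables. An analyst who does not would have to choose a denominator without guidance, possibly after seeing the data.

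**Working it through.** **1. The plan's own figure.** Section 10.2 calls the expansion positive if at least 11 of 15 evaluable patients reach threshold. At a true rate of 50%, the probability is (1365 + 455 + 105 + 15 + 1)/32768 = 1941/32768 = 0.0592 (stated 5.9%). At 80%, the exact binomial tail is 0.8358 (stated 83.6%). Both reproduce. The rule is already defined on evaluable patients, so nothing below changes it.

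**2. Which set each expansion analysis uses.**

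| Analysis | Section | Set stated |
|---|---|---|
| Cycle 2 drug level | 10.2, 10.4.2 | evaluable patients |
| DLT evaluability | 10.3.1 | any treated patient with a related DLT within 21 days |
| DLT accrual rule | 10.4.4 | patients enrolled |
| Objective response | 10.3.2 | own set; keeps patients who progress in cycle 1 |
| Non-target response | 10.3.3 | own set |
| Adverse events by grade | 10.1.2, 10.4.3 | none, beyond the expansion cohort |
| PFS, OS | 10.4.9 | none, beyond patients in the expansion cohort |

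The phrase expansion cohort does not settle the last two rows. The cohort table in 2.4 describes the cohort as up to 15 eligible and evaluable patients treated to assess safety, and 10.4.4 calls it a 15-patient cohort. With 5 replacements, however, 20 could be treated.

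**3. What the DLT provisions leave open.** The endpoint is all adverse events by grade. The DLT sentence settles who is evaluable for DLT, and 10.4.4 settles whether accrual continues. Neither sets the denominator of an adverse event table. Section 3.1.1 exempts several toxicities from being DLTs, including infusion reactions up to grade 3. It does count as a DLT an inability to start cycle 2 within 2 weeks because of drug-related events, which would catch some discontinuations. Non-DLT events in a patient who leaves for progression, withdrawal or death from disease remain uncovered.

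**4. Size under the literal reading.** With k patients left out for every 15 analysed, the omitted share is k/(15 + k).

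- k = 1: 1/16 = 6.3%
- k = 3: 3/18 = 16.7%
- k = 5, the full replacement allowance: 5/20 = 25%

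The documents give no cycle 1 drop-out rate. If a fraction q leaves before cycle 2, the expected number treated per 15 evaluable is 15/(1 − q): 16.7, 18.8 and 21.4 for assumed q of 10%, 20% and 30%. The allowance covers progression only. Departures for toxicity or withdrawal have no stated replacement rule, so the documents do not bound that share.

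**5. Effect on an adverse event rate (assumed counts).** Suppose 3 of the 15 have a given event: 3/15 = 20%. With 5 omitted patients restored, the rate lies between 3/20 = 15% (none had it) and 8/20 = 40% (all had it). The direction is therefore not fixed for every event. For an event that itself prevents cycle 2, those who stopped because of it are never in the restricted set, so its rate can only be understated.

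**6. PFS and OS, if the cycle 2 set were used.** Both clocks start at first treatment (6.3.5, 6.3.8). The first cycle 2 LMB-100 dose falls on day 21 + 4 = 25, or day 23 if the cycle starts the permitted 2 days early. Progression ends protocol therapy (3.5). PFS at about week 3 would then be 100% by construction, against at most 15/20 = 75% in all treated if 5 progressed before cycle 2.

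**The case against.** The strongest reply is that the sentence is only misplaced. Read with 10.2 and 10.4.2, it says who counts towards the 15 for the drug-level endpoint. Other text supports this:

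- 10.3.1 itself says "Any patient who receives any study drug treatment and experiences a DLT related to study drug within 21 days of initial treatment is evaluable", without limiting that to escalation.
- 10.4.4 uses enrolled patients. Because DLTs are cycle 1 events, that rule works only if cycle 1 toxicity is counted.
- Adverse events are documented from Study Day 1 (6.1), and all patients are followed to death for survival (Study Calendar footnotes).

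This stands as evidence of probable intent. It shows that the data will exist and that DLT monitoring is protected. It does not state who enters the adverse event tables.

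A reader might infer two stronger claims, and the documents support neither. The first is that the cycle 2 set is the expansion's only analysis set. It is not: 10.3.2 and 10.3.3 define response sets, and 10.3.2 says "Patients who exhibit objective disease progression prior to the end of cycle 1 will also be considered evaluable". The second is that PFS and OS carry immortal-time bias. Section 10.4.9 refers to patients in the expansion cohort, without the word evaluable that the plan uses for the drug-level endpoint. The bias follows only if an analyst carries the cycle 2 set over.

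The size is also open to challenge. Re-evaluation is every 6 weeks in 6.3 and about every 9 weeks in the Study Calendar, and 10.2 expects progression at restaging after 2 cycles. Progression found before cycle 2 would be off schedule, so 5 such patients is an upper-end case.

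**Conclusion.** The point holds as a moderate ambiguity in a stated secondary safety endpoint. Section 10.3.1 gives an all-treated report for escalation and none for the expansion, and its literal wording would leave treated patients who stop or die in cycle 1 out of the expansion adverse event tables. That reading conflicts with 10.4.4 and with the expansion's safety purpose, so the sections must be reconciled. For PFS and OS the finding is narrower: no set is named, and using the cycle 2 set would require patients to reach cycle 2 in order to be counted from first treatment.

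The 25% figure (5 of 20) assumes that the whole replacement allowance is used and that the literal reading is applied. It is an illustration and not a forecast. The primary decision rule and the response sets are unaffected.

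**What to change.** In 10.3.1, limit the cycle 2 sentence to the drug-level endpoint and add a sentence such as: *All expansion participants who receive any dose of tofacitinib or LMB-100, including those later replaced, are included in the adverse event tables and in the PFS and OS analyses.* Cross-refer to it from 10.4.3 and 10.4.9.

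The cost is one added sentence and two cross-references. Sample size, data collection and the 11-of-15 rule stay as they are. The downside is that adverse event, PFS and OS figures may look slightly less favourable than in the restricted set.
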